9 STUDY TREATMENT, DESCRIPTION AND ALLOCATION

9.1 Investigational Medicinal Products (IMP) Description

All study medications will be dispensed by and returned to a qualified Independent Dispenser designated by the Principal Investigator. The Independent Dispenser will not be involved in performing any of the clinical assessments (IGA, lesion count, evaluation of signs and symptoms of local irritation, or evaluation of safety).

The IMP will be dispensed only from the institution(s) approved by an Institutional Review Board.

The following treatments will be self-administered or administered by the Subject's caregiver during this study.

The IMP supplied in 45 gm pumps, by the Sponsor will consist of the following:

Test Product:	TRIFAROTENE CREAM, 0.005% (Manufactured by Actavis Laboratories, Salt Lake City, UT for Teva Pharmaceuticals, Inc.)
Reference Product:	AKLIEF® (TRIFAROTENE 0.005% CREAM) (GALDERMA LABORATORIES, L.P., USA)
Placebo Control:	Placebo (Vehicle) topical cream (Manufactured by Actavis Laboratories, Salt Lake City, UT for Teva Pharmaceuticals, Inc.)

9.2 Storage and Handling Conditions

- Store at 20 to 25°C (68 to 77°F) with excursions permitted to 15° to 30°C (59° to 86°F) in a secured, authorized access area at the investigative site.
- Keep away from heat.
- Keep out of reach of children.

9.2.1 Packaging, Blinding and Labeling

[REDACTED] The labeling and packaging scheme will be outlined in a separate document by the Sponsor. The label content of IMP products will meet the requirements of ICH GCP guidelines, country specific guidelines and study protocol.

[REDACTED]. The study product will be packaged identically; an individual pump of study product (i.e., either Test, Reference or Placebo) will be packaged, as a “subject kit”. Each subject will be assigned to one kit.

[REDACTED] all subjects consented and screened into the study will be assigned a “Subject Number.” The Subject Number is the only subject identifier for subjects who are screened into the study (i.e., after being consented). The Subject Number is assigned, when a subject is screened into the study (i.e., after being consented). The study subject numbers will be assigned to study subjects sequentially in the order in which study subjects are enrolled into the study. [REDACTED]

[REDACTED]

Both the subject number and randomization number will be entered into the subject's eCRF. Each time a subject is dispensed study product (i.e., at Visit 1, and 2 or 3 as required, and when applicable unscheduled visit), [REDACTED]

[REDACTED]. Each subject will maintain the same subject number and treatment assignment throughout the study.

A label will be attached to each of the pumps of study product. The label will include at least the following information: Protocol number, subject number, study product kit number, space for subject's initials, statement that the study product is for Investigational Use only, space for dispensing date and the Sponsor's name. In addition, all subjects will be provided with written instructions on how to use the study product. .

[REDACTED] The study medications will be shipped to the Investigator's site from a centralized location.

This is a double-blind clinical endpoint bioequivalence study. The IMP will be labeled and packaged such that neither the Subject nor any Investigator or study can identify the treatment. The Investigator, staff at the study site, study monitors, and data analysis/management personnel will be blinded to the treatment assigned to the subject. [REDACTED]

[REDACTED]. The subject will be requested not to discuss the appearance of the study medication with the Investigator or study staff [REDACTED]

The Principal Investigator will be responsible for ensuring that all study products are stored in a locked, secure location, with access limited to the Investigator and his/her designee(s). An accurate inventory of the study medication will be maintained in accordance with federal regulations.

To ensure that information that could potentially bias handling of data is not disclosed, the packaging team will hold the randomization scheme until after database lock. At the end of the study, after all the clinical data has been entered and the study database has been locked, a copy of the randomization schedule will be sent to the statistician [REDACTED]

9.2.2 Randomization

The randomization schedule for this study will be generated [REDACTED]

[REDACTED] A copy of the randomization scheme (respective to that site) will be retained at the study site following the completion of the study and should be available to

regulatory authority inspectors at the time of site inspection to allow for verification of the treatment identity of each subject.

9.2.3 Subject Screening Number

Once a subject has signed the ICF, the subject will be assigned with a screening number, starting with three-digit site numbers followed by three-digit number starting from 001 in chronological order of screening in each site (e.g., 01001 for the first subject who signed ICF and screened at site 01).

9.3 Treatment Assignment

The subject study identification number will correspond to a computer-generated randomization schedule assigning that number to one of the three study treatment groups.

The subject numbers at the site will correspond to the order in which subjects are enrolled into the study.

9.4 Administration of Investigational Medicinal Product

At Visit 1, IMP will be dispensed by the Independent Dispenser to randomized Subjects along with a diary. Each Subject will also receive written study instructions, which detail the proper application method of the IMP and general study instructions. Before each application, Subject should wash their face with a non-medicated cleanser (provided by the Sponsor), and pat dry. Skin should be allowed to dry for 20-30 minutes before applying study medication. The skin should be completely dry in order to minimize possible irritation. The Independent Dispenser will instruct the Subject not to open the IMP containers at the study center and to apply enough product to lightly cover the entire affected areas of the face once daily in the evening, preferably at bedtime.

Contact with the eyes, lips/mouth, angles/corners of the nose, open wounds and other mucous membranes should be avoided. Hands should be washed before and after applying the study medication. IMP should be applied in this manner daily for 84 days.

Subjects will be required to use diaries to document the date and time of application of study treatments, any missed treatments and the occurrence of all adverse events.

Subjects will be instructed not to bathe, shower, wash or swim for at least 4 hours after the application of the IMP.

9.5 Assessment of Compliance

Compliance with scheduled application of IMP will be determined from the Subject’s diary. The

Subject will be instructed to use the diary to document all doses taken by checking the yes or no box for the appropriate date. In addition, Subjects will be instructed to document all concomitant medication and AEs on the diary. Used IMP will be returned to the study site at each scheduled visit or Early Discontinuation Visit or as applicable. If the subject does not return the Diary, compliance cannot be determined.

9.6 Investigational Medicinal Product Accountability

It is the responsibility of the Principal Investigator to ensure that the current disposition of the IMP is maintained at each study site where IMP is inventoried and dispensed. When a drug shipment is received at a study site, the Principal Investigator or the Principal Investigator's Designee (for the purposes of this study the Independent Dispenser) must inventory the drug and sign the receipt form provided with the shipment. The receipt form should be emailed as per instructions provided on the receipt. A copy of the receipt should remain at the site.

The Principal Investigator at each site is responsible for ensuring that all investigational products are stored in a locked, secure location, with access limited to the Investigator and his/her designee(s). The Investigator will not supply study test articles to any person not enrolled in this study, or to any physician or scientist except those named as sub-investigators.

A **Drug Accountability Log** will assist study site staff in maintaining inventory records of study drug and is necessary for monitoring. An accurate inventory of the IMP will be maintained by the Independent Dispenser, in accordance with federal regulations. Subject's must return used, partially used or unused IMP to the Independent Dispenser, at the end of the study, (Visit 4) so that any remaining drug supplies can be accounted for and noted in the Drug Accountability Log.

The certified copy of Drug Accountability Log must be provided to the study monitor at the conclusion of the study and the original should remain at the study site.

Once the site has been notified that they may do so, all unused investigational product and empty or partially used pumps of investigational product, other than the randomly selected for retention samples, will be returned to the Drug Labeling, Packaging and Shipping Facility (Actavis Laboratories UT, Inc.) or be destroyed at the site after study close-out following approval from the Sponsor, and final drug accountability is reconciled.

9.7 Retention of Study Drug Samples

Enough of the study drug will be retained amongst the sites participating in the study to meet the sample retention requirements of the US-FDA 21 CFR 320.38, 320.63, Guidance for Industry “Compliance Policy for the Quantity of Bioavailability and Bioequivalence Samples Retained Under 21 CFR 320.38(c)” and the Guidance for Industry “Handling and Retention of BA and BE Testing Samples”.

[figure not shown]
Samples of study drug will be randomly selected at the investigational site, in accordance with 21 CFR 320.38, 320.63, Guidance for Industry “Compliance Policy for the Quantity of Bioavailability and Bioequivalence Samples Retained Under 21 CFR 320.38(c)” and the Guidance for Industry, “Handling and Retention of BA and BE Testing Samples”, regarding retention of study drug samples. and 21 CFR 320.36 for requirements for maintenance of records of bioequivalence testing. In addition, the Investigators should follow the procedures of 21 CFR 58 and ICH E6, “Good Clinical Practice: Consolidated Guideline”, for retention of study records and data in order to conduct their studies in compliance with Good Laboratory Practices (GLP) and Good Clinical Practices (GCP).

Each reserve sample will be stored under conditions consistent with product labeling [Store at room temperature between 20°C - 25°C (68°F to 77°F)] and with access limited to authorized personnel. Each reserve sample will be retained for a period of **at least 5 years** following the date on which the application or supplemental application is approved, or, if application is not approved, at least 5 years following the date of completion of the study.

The number of subject kits kept for retention will be noted on the study product accountability form, as a retention sample, in addition to the retention sample log. The study site PI is responsible for storage of retention samples while at the site, until shipment to a third-party repository.

To ensure samples are not confused with investigational product for subject use and to ease the storage burden at a site, the randomly selected retention samples of investigational product will be transferred by the sites to an independent biorepository vendor, an independent third-party storage facility for long term storage. To ensure compliance with product specific storage requirements, the original label should not be covered with a new shipping label.

[REDACTED]

[REDACTED]

The samples can be retrieved from the storage facility at any time upon FDA notification of the visit or during a pre-approval inspection conducted by authorized FDA personnel. The samples can be returned to the investigational site or submitted to the place identified in the agency's request. The request has to be sent directly to an independent biorepository vendor by email or fax from the site. The Sponsor (Teva Pharmaceuticals, Inc.) [REDACTED] must be notified, and copies of documentation should be sent to the individuals listed below:

Retention Samples Storage Facility	Sponsor	Clinical Research Organization:
[REDACTED]	[REDACTED]	[REDACTED]
[REDACTED]	[REDACTED]	[REDACTED]

9.8 Return of Clinical Supplies

Except for the retention samples, all used and unused pumps of IMP may be returned to the Drug Labeling, Packaging and Shipping Facility (Actavis Laboratories UT, Inc.) for destruction or be destroyed at the site after study close-out following approval from the Sponsor, and final drug accountability is reconciled.

It is important that retention samples and all used and unused pumps of IMP not be returned to [REDACTED] or the Sponsor (Teva) at the end of the study.

9.9 Additional Supplies Provided by The Sponsor

[REDACTED]

[REDACTED]

[REDACTED]

10 STATISTICAL METHODS

10.1 Scientific and Statistical Considerations of the Study Design

The study was designed following FDA Draft Guidance on Trifarotene Recommended May 2021⁶ and FDA Draft Guidance on Adapalene; Benzoyl peroxide Gel; topical, Recommended Dec 2016; Revised Nov 2018, Nov 2019⁷ and Guidance for Industry -Acne Vulgaris: Establishing Effectiveness of Drugs Intended for Treatment, May 2018⁴.

10.1.1 Sample Size Rationale

Sample size calculations are based on information from a Medical Review¹¹ for developing a bioequivalence study comparing Trifarotene cream 0.005% after 12 weeks of treatment.

[REDACTED]

[REDACTED]

[REDACTED]	[REDACTED]	[REDACTED]	[REDACTED]	[REDACTED]
[REDACTED]	[REDACTED]	[REDACTED]	[REDACTED]	[REDACTED]
[REDACTED]	[REDACTED]	[REDACTED]	[REDACTED]	[REDACTED]

[REDACTED]

[REDACTED]

[REDACTED]

[REDACTED]

10.1.2 Unblinding Procedures

This is a Randomized, Double-blind, Three-Arm, Placebo Controlled, Parallel design, multi-centre study. Subjects will be randomly assigned [REDACTED] to receive the test product, the reference product and the vehicle (placebo) control. The randomization assignment will be generated using SAS® by [REDACTED]. The treatment each subject will receive will not be disclosed to the Investigators, study center personnel, subject, sponsor, or CRO involved in the study conduct, monitoring, data review or analysis.

[REDACTED]

If necessary, for the safety and proper treatment of the subjects, the Investigator can unblind the subject's treatment assignment to conduct appropriate follow-up care. Whenever possible, the Sponsor or medical monitor will be notified before unblinding the study medication. The date and signature of the person breaking the code as well as the reason for breaking the code and any associated AEs will be recorded in the subject's source documentation.

The Investigator, staff at the study site, study monitors, and data analysis/management personnel will be blinded to the treatment assigned to the subject, with the exception of the Independent Dispenser. The study site will have at least one Independent Dispenser. The role of the unblinded Independent Dispenser will be to dispense and collect study medication to/from the subjects, maintain dispensing records, and ensure the study medication logs are complete and accurate. The subject will be requested not to discuss the appearance of the study medication with the Investigator or study staff outside of the Independent Dispenser. Independent dispenser should not participate in any activities other than the activities defined in this section.

In case of an emergency, if the details of the study drug are required for management of an emergency as per the opinion of Investigator, the Investigator can unblind the product that is received by the subject during the study. In case of non-emergency condition that requires study drug information for management of condition as per Investigator's opinion, the Investigator should obtain Sponsor or medical monitor approval in writing prior to breaking of the blind. [REDACTED]

[REDACTED] It is recommended that all attempts should be made to maintain the study blind. However, in case that unblinding is performed, the reason for breaking the blind must be clearly documented in the source documentation and Case Report Form (CRF) and the subject must be discontinued from the study.

The date on which the code was broken together with the identity of the person responsible must also be documented.

The treatment assignments will remain blinded until the final database is locked.

10.1.3 Significance Level

All statistical tests will be two-sided at a significance level of $\alpha = 0.05$, unless otherwise indicated. No adjustment will be made for multiplicity.

10.2 Datasets to be Analyzed

Three analysis populations will be used in the analysis of the clinical data:

[Redacted]

[Redacted]

[Redacted]

[Redacted]

[Redacted]

[Redacted] proper administration of the treatment or accurate evaluation of its effectiveness.

[Redacted]

[Redacted]. In addition, subjects whose condition or symptoms worsens and require alternate or supplemental or rescue therapy for the treatment of their condition during the treatment phase of the study should be discontinued, included in the mITT and PP population analysis using LOCF, and provided with effective treatment. The use of supplemental medicines and rescue medicine will be per standard of care (SOC) per medical judgement of the Investigator. All supplemental and rescue medicines will include name, dose, frequency of administration, start and end dates, which is supplied to discontinued subjects for worsening of conditions.

[figure not shown]
[Redacted]

[Redacted]

[Redacted] If subject makes the decision to withdraw or discontinue from the study, then the reason for withdrawal/discontinuation will be coded as “lack of treatment effect” (LOTE).

[Redacted]

A shift table will be provided for any subject that has been discontinued with the reason of lack

of treatment effect to show changes from screening/baseline to time of discontinuation (last observation).

10.3 Measures

At each visit, beginning at Visit 1, an Investigator will assess the overall status of the Subject's facial acne vulgaris using the Investigator's Global Assessment (IGA) and the Lesion Counts.

Local irritation/application site reactions such as erythema, dryness, burning/stinging, erosion, edema, pain and itching will be recorded at each visit to allow a comparison between treatment groups. A detailed scale is presented.

10.3.1 Demographics and Screening/Baseline/Randomization Characteristics

Demographic and screening/baseline/randomization characteristics will be evaluated for comparability across treatment groups for the mITT, PP, and safety populations. Continuous variables will be analyzed with an analysis of variance with factors of treatment and investigational site. Categorical variables such as gender, ethnicity, and race will be analyzed with a Cochran-Mantel-Haenszel test, stratified by investigational site.

10.3.2 Safety Assessment

The extent of exposure will be summarized using descriptive statistics. No inferential analyses are planned.

Incidence of all adverse events reported during the study will be summarized using the MedDRA dictionary by treatment group, body system, severity, and relationship to study drug. The comparability of the Test and Reference treatment groups for the frequency and severity of any adverse event that occurs in at least 5% of the subjects in either treatment group will be evaluated using categorical methods.

The concomitant medications used will be summarized by treatment group.

Application site reactions such as erythema, dryness, burning/stinging, erosion, edema, pain and itching will be summarized for the safety population by treatment group and study visit using frequencies and percentages of subjects.

Safety analyses will be performed on the safety population. All safety data will be listed by treatment and Subject in data listings.

10.3.3 Efficacy Assessment

10.3.3.1 Primary Endpoints

The primary efficacy endpoints are the mean percent change from screening/baseline to week 12 in the inflammatory (papules and pustules) and in the non-inflammatory (open and closed comedones) lesion counts.

10.3.3.2 Test of Clinical Equivalence

The evaluations of clinical equivalence will be performed for the PP population.

For the primary efficacy assessment, the two-sided, 90% confidence interval on the test/reference ratio of the mean percent change from screening/baseline to week 12 in each lesion type will be calculated using Fieller's method and the pooled variance estimate (MSE) obtained from a two-way Analysis of Variance (ANOVA) of the Test and Reference results. The statistical model for the ANOVA will contain terms for treatment and center. If the skewness of the residuals from the ANOVA is outside of -2 to 2, then a nonparametric approach will be used to obtain the confidence intervals. Bioequivalence will be established if the 90% confidence intervals for the ratio of test/reference means, for both inflammatory and non-inflammatory lesion counts, are contained within the interval [0.80, 1.25] using the per protocol (PP) population.

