7.2 Lesion Counts

At each study visit, beginning at Visit 1, an Investigator will assess by counting the number of open and closed comedones (non-inflammatory lesions), pustules and papules (inflammatory lesions) and nodulo-cystic lesions from the jaw line to the hairline. All lesions will be counted,

[REDACTED]

including those present on the nose. Counts of nodules and cysts should be reported separately and not included in the inflammatory or non-inflammatory lesion counts. A papule with a pustule on its apex will be counted as a pustule. [REDACTED]

[REDACTED]

To be included in the study, subjects must have ≥ 25 non-inflammatory lesions (i.e., open and closed comedones) AND ≥ 20 inflammatory lesions (i.e., papules and pustules) AND ≤ 2 nodulocystic lesions (i.e., nodules and cysts), at screening/baseline on the face.

Lesion Type	Definition
Closed Comedone	Non-inflammatory lesion; whitehead, skin-colored or slightly inflamed “bump” in the skin
Open Comedone	Non-inflammatory lesion: blackhead, surface of the plugged sebaceous follicle has a blackish appearance
Papule	Inflammatory lesion: a small (≤ 5 mm in diameter), solid palpable lesion, usually with inflamed elevation of the skin that does not contain pus
Pustule	Inflammatory lesion: a small (≤ 5 mm in diameter), inflamed skin swelling that is filled with pus
Nodules	Large, hard bumps under the skin's surface
Cysts	Similar to a nodule, but is pus-filled, and ≥ 5 mm in diameter

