5. HYPOTHESES TESTING

Hypothesis of Equivalence

A two-sided, 90% confidence intervals on the test/reference ratio for mean percent change from Baseline in the inflammatory and non-inflammatory lesion counts will be constructed using Fieller's method. The estimates of treatment means and standard errors will be obtained from a two-way Analysis of Variance (ANOVA) of the Test and Reference results, using a statistical model containing terms for treatment and center. Non-parametric methods will be considered if the skewness factor for the residuals from the ANOVA model is outside the range -2 to +2.

Bioequivalence will be established if the 90% confidence intervals for the ratios of test/reference means for both the inflammatory and non-inflammatory lesions are contained within the interval [0.80, 1.25].

Hypothesis of Superiority

The null hypothesis to be tested is that there is no difference in the mean percent change (reduction) from baseline in the inflammatory and non-inflammatory lesion counts between the active treatment and the Vehicle treatment. The hypothesis testing will be performed separately for the Test treatment versus the Vehicle treatment and for the Reference treatment versus the Vehicle treatment using ANOVA under assumption of normal error and homogeneity of variance. Only data for the relevant two treatment arms will be included in each ANOVA. Similarly to bioequivalence, non-parametric methods will be considered if the skewness factor for the residuals from the ANOVA model is outside the range -2 to +2.

Superiority will be established if the mean percent change (reduction) from Baseline in both the inflammatory and non-inflammatory lesion count for each active treatment is greater than, and statistically different from ($p < 0.05$, two-sided), that for the Vehicle.

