7.3 Demographic and Baseline Characteristics

Demographic characteristics will include:

- age;
- gender;
- race;
- ethnicity;

Baseline characteristics include:

- Time since acne vulgaris diagnosis (years)

- Baseline inflammatory lesion count (i.e papules and pustules)
- Baseline non-inflammatory lesion count (i.e. open and closed comedones)
- Baseline nodulocystic count (i.e. nodules and cysts)
- Baseline IGA score
- Baseline height, weight and body mass index (BMI)

Descriptive statistics will be presented for age (years), height, weight, BMI, time since diagnosis (years) and lesion counts. Frequency counts and percentages will be presented for race, ethnicity and IGA. Height will be reported in centimeters and weight in kilograms.

Age will be derived from Informed Consent Signed Date and Date of Birth as the number of whole years between those two dates.

Demographic and baseline characteristics will be evaluated for comparability across treatment groups in the following manner. Continuous variables will be analyzed with an ANOVA with factors of treatment and investigational site. Overall p-value for the global null hypothesis of all groups being equal will be displayed. Categorical variables will be analyzed with a Cochran-Mantel-Haenszel stratified by investigational site. For IGA score “row mean scores differ” CMH statistic will be used, while for all other parameters “general association” CMH statistic will be used.

These analyses will be performed for Safety, mITT, and PP populations.

All demographic and baseline characteristics will be listed.

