7.6.2 Analyses of Primary Endpoint

At each study visit, beginning at Visit 1, an Investigator will count the number of open and closed comedones (non-inflammatory lesions), pustules and papules (inflammatory lesions) and nodulo-cystic lesions. Lesion counts will be recorded in the CRF.

Missing Week 12 assessments will be imputed as follows. In the mITT analysis, if a subject discontinues the study prior to Week 12 or misses the Week 12 assessment for any other reason, the LOCF rule will be used to impute the number of lesions. In the PP analysis, if a subject discontinues the study prior to Week 12 due to lack of treatment effect [REDACTED], the LOCF rule will be used to impute the number of lesions. If a subject is missing the Week 12 assessment for any other reason, the subject will be excluded from the PP population.

The LOCF rule will be applied as follows: the last available post-baseline lesion count of the given type will be carried forward to impute the missing Week 12 assessment of the same type. Subjects who do not have any post-baseline lesion counts of a certain type will be excluded from the analysis of that type.

The baseline lesion count will be defined as the results from the latest examination prior to the first application of the study medication. For each post-baseline visit the change from baseline and percent change from baseline in the number of inflammatory and non-inflammatory lesions will be calculated. The baseline value, visit value and percent change from baseline at the visit will be analyzed using descriptive statistics and will be tabulated by visit and treatment group.

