7.6.2.1 Analysis of clinical equivalence of test and reference treatments

To show the clinical equivalence, estimates of mean percent change from baseline in the inflammatory and non-inflammatory lesion counts will be calculated for the Test and Reference treatment, and then the 90% CI for the mean ratio will be constructed using Fieller's method. Bioequivalence will be established if the 90% confidence intervals for the

ratios of Test/Reference means are contained within the interval [0.80, 1.25] for the PP population for both lesion types (inflammatory and non-inflammatory).

To this end, first an ANOVA model will be fit (separately for each lesion type) with percent change from baseline in lesion count as outcome and treatment, center and treatment-by-center interaction as factors on the data from Test and Reference treatments only (excluding Vehicle subjects). If the treatment-by-center interaction factor is not significant at the 0.05 level, the model will be rerun without the interaction term. Treatment means and standard errors will be estimated from this model. Then Fieller's formula will be applied; covariance between the treatment means will be assumed to be 0. See [Appendix 11.2](#) for complete description of the Fieller's formula.

A non-parametric rank based ANOVA will be considered when the data is highly skewed. The evaluation of skewness, (using SAS[®] PROC UNIVARIATE) will be performed using the residuals from ANOVA and if the skewness statistic is less than -2 or greater than +2, the analysis will be performed on the ranks of the percent change in the inflammatory lesion count values.

Analysis of bioequivalence will be performed on the PP population

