7.6.2.2 Analysis of superiority to vehicle control

The analysis of superiority will be performed separately for the Test treatment versus the Vehicle treatment and for the Reference treatment versus the Vehicle treatment and separately for the inflammatory and non-inflammatory lesions. Each of these analyses will be performed using an ANOVA model with percent change from baseline in the lesion count as outcome and treatment, center and treatment-by-center interaction as factors. If the treatment-by-center interaction factor is not significant at the 0.05 level, the model will be rerun without the interaction term. The model will be fit on data from the Test and Vehicle treatment for analysis of superiority of the Test treatment and separately on data from the Reference and Vehicle treatment for analysis of superiority of the Reference treatment. From this model, the least square (LS) mean estimate for each treatment group with the 95% CI will be calculated; further, an estimate of the LS mean difference between the active treatment (Test or

Reference) and Vehicle with 95% CI and the p-value for test of no difference will be calculated.

Superiority will be established if the mean percent change from Baseline (reduction) for each active treatment and each lesion type is estimated to be greater than, and statistically significantly different from ($p < 0.05$ for test of no difference) that for the Vehicle, for the mITT population.

Analysis of superiority will be performed on the mITT population.

A non-parametric rank-based ANOVA will be considered under the same circumstances as for the analysis of bioequivalence.

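### The primary equivalence and superiority models omit the baseline lesion count; the analysis is valid, but precision may be lost at almost no saving

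*Protocol*

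**What the plan says.** The endpoint is set in Protocol 10.3.3.1: "The primary efficacy endpoints are the mean percent change from screening/baseline to week 12", separately for inflammatory and non-inflammatory lesions.

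Model terms:

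- Protocol 10.3.3.2 (equivalence): "The statistical model for the ANOVA will contain terms for treatment and center". Protocol 10.3.3.3 (superiority) has the same sentence.
- SAP 5 describes equivalence estimates obtained "using a statistical model containing terms for treatment and center".
- SAP 7.6.2.1, the operative equivalence model, takes "treatment, center and treatment-by-center interaction as factors on the data from Test and Reference treatments only". The interaction is dropped if not significant at 0.05.
- SAP 7.6.2.2, the operative superiority model, is an "ANOVA model with percent change from baseline in the lesion count as outcome and treatment, center and treatment-by-center interaction as factors", with the same rule for the interaction.
- The PROC GLM code in SAP 11.2 matches these two sections.

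Baseline count:

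- Protocol 7.2 makes it an entry condition ("To be included in the study, subjects must have" at least 25 non-inflammatory and at least 20 inflammatory facial lesions).
- SAP 7.6.2 defines it: "The baseline lesion count will be defined as the results from the latest examination prior to the first application of the study medication".
- SAP 7.3 lists "Baseline inflammatory lesion count (i.e papules and pustules") and its non-inflammatory counterpart among the characteristics compared across arms.

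Apart from forming the percent change, descriptive tables and that comparison, the count is not used. Neither document says why it is left out of the models.

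**The concern.** The residual variance sets the width of the 90% Fieller interval, which must lie inside [0.80, 1.25] for both lesion types. It also drives the four superiority tests: two active arms, each against vehicle on two lesion types. The plan needs all six results to succeed, so unexplained variance that a recorded baseline value could remove is worth removing.

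Two further features make the omission worth raising. SAP 7.3 tests baseline counts for comparability, but the plan gives no way to act on an imbalance. And equivalence is decided in the per-protocol population. SAP 7.6.2 excludes from it subjects who lack a Week 12 assessment for reasons other than those for which it allows carry-forward. Randomization alone therefore does not guarantee baseline balance in that set.

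**Working it through.** **No plan figure to reproduce.** Sample size, means, SDs, power and allocation are redacted (Protocol 10.1.1, SAP 3.2), and no correlation between baseline count and percent change is given. Every figure below rests on an assumed within-arm correlation rho.

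**Step 1: effect on precision.** With a linear baseline covariate, residual variance is multiplied by (1 − rho²) and the SE by √(1 − rho²). The equivalent increase in sample size is 1/(1 − rho²) − 1.

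| rho | SE factor | SE reduction | Equivalent extra subjects |
|---|---|---|---|
| 0 | 1.000 | 0% | 0% |
| 0.1 | 0.995 | 0.5% | 1% |
| 0.2 | 0.980 | 2.0% | 4% |
| 0.3 | 0.954 | 4.6% | 10% |
| 0.4 | 0.917 | 8.3% | 19% |

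**Step 2: superiority power.** For a test with planned power P, the adjusted power is Φ((1.96 + z_P)/√(1 − rho²) − 1.96). From an assumed 80% it becomes 80.4%, 81.6%, 83.6% and 86.4% at rho 0.1, 0.2, 0.3 and 0.4. From an assumed 90% it becomes 90.3%, 91.1%, 92.5% and 94.3%.

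**Step 3: equivalence interval.** This uses the simplified Fieller formula in SAP 11.2. Assumed inputs: both means a 50% reduction, SD 50, 250 per arm, 480 error degrees of freedom, t = 1.648. Zero covariance is kept here for illustration.

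- rho 0: SE = 50/√250 = 3.162; g = 1.648² × 3.162²/50² = 0.0109; half-width before scaling = (1.648/50) × √(2 × 3.162² − 0.0109 × 3.162²) = 0.1470. Interval (1 ∓ 0.1470)/(1 − 0.0109) = 0.862 to 1.160.
- rho 0.3: SE = 3.162 × 0.954 = 3.017; g = 0.0099; half-width 0.1403. Interval 0.868 to 1.152.

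Simulated power for one lesion type under the same assumptions, with a true ratio of 1, is about 59% at rho 0, 60% at 0.1 and 65% at 0.3. With 350 per arm it is about 80%, 80% and 84%.

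**Step 4: chance imbalance.** The shift in a mean difference is the slope times the imbalance, that is, rho × SD of the outcome × imbalance in baseline SD units. With 250 per arm, one standard error of imbalance is √(2/250) = 0.089 SD. With SD 50 and mean 50, the ratio moves by 0.3 × 50 × 0.089/50 = 2.7% at rho 0.3, by 0.9% at rho 0.1, and not at all at rho 0.

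**Step 5: is rho likely to be large?** Percent change already divides by baseline, so only residual dependence counts. A simulation assumed skewed baselines of at least 20, a response proportional to the true count, and Poisson follow-up counts. It gave rho of about 0.00 when baseline had no counting noise and about −0.07 when it did. At −0.07 the SE falls by about 0.2%. A larger gain needs the proportional response itself to vary with baseline severity, which the documents do not address.

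**The case against.** The strongest reply is that the endpoint already uses baseline. Each count is divided by its own baseline, and under a proportional response almost nothing is left for a covariate to explain. That stands: the documents contain no evidence of a material correlation, and the simulation above falls below the lowest non-zero value in the table.

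A reader might infer that the planned intervals and tests are less precise than the data allow, that the entry thresholds and regression to the mean ensure a correlation, or that chance baseline imbalance passes straight into the ratio. The documents support none of these. The first two need a correlation that is nowhere stated. The third holds only in proportion to the baseline slope. Nor is there a validity problem: leaving out a baseline covariate does not bias a randomized comparison or inflate its type I error. The per-protocol selection weakens the appeal to randomization, but adjusting for one observed variable gives only partial protection there.

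Protocol 10.1 says the design follows FDA draft guidances. They may prescribe treatment and center as the model terms. That cannot be checked from the documents, which quote no model terms and nowhere say that a covariate is barred. It is a reason to offer a supportive analysis as an alternative, not a reason to drop the point.

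**Conclusion.** The point stands as a low-cost improvement, not as an error. The same-type baseline count is missing from every primary model in both documents, is available for every eligible subject, and its omission is not explained. The possible gain runs from nothing at rho 0 to an 8.3% smaller SE at rho 0.4, the top of the tabulated range, and the lower end is plausible for a percent-change outcome. If rho is near zero, adjustment costs one error degree of freedom per model. The effect on the actual equivalence decision cannot be stated, because the planning values are redacted; the power and interval figures are illustrations under assumed means, SDs and sample sizes.

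**What to change.** Before unblinding, amend the SAP as follows:

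1. Add the baseline count of the same lesion type as a covariate in 7.6.2.1, 7.6.2.2 and the code in 11.2. Keep the pooled center term and the stated treatment-by-center step.
2. Estimate LS means at the common baseline mean. The adjusted means share an estimated slope, so replace the assumed zero covariance with the model covariance of the LS means, using the general Fieller formula already printed in 11.2.
3. State how the covariate enters the rank-based ANOVA fallback, for example as the raw or the ranked baseline count.
4. Keep the unadjusted ANOVA as a sensitivity analysis, and list the change in SAP section 8.

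If the cited guidances fix the primary model, leave it as it is, say so, and pre-specify the baseline-adjusted model as the supportive analysis.

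The cost is one error degree of freedom per model, the extra output needed for the covariance, a rule for the fallback and a second set of runs. No new data, visits or subjects are needed.
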